- Difficulty swallowing, hoarseness, and cough severity, each assessed on a 0-to-5 ordinal severity scale
- Burping frequency, assessed on a 0-4 frequency scale

In addition, Sleep Disturbance due to GERD symptoms - including difficulty falling asleep and the number of nighttime awakenings during the prior evening will be recorded each morning.

Heartburn severity will be assessed once daily in the evening, before bed, on a 0-to-5 ordinal severity scale.

The following patient-reported items will be assessed once weekly:

- Degree of Relief of heartburn, regurgitation, and overall GERD symptoms, each rated on 7-point balanced ordinal scale (1=significantly relieved, 4=unchanged, 7=significantly worse); Degree of Relief of heartburn, regurgitation, and overall GERD symptoms on 7-point patient global impression of change scale (compared to before you started the study; 1=significantly relieved, 4=unchanged, 7=significantly worse)
- Bothersomeness of heartburn, regurgitation, and overall GERD symptoms, each rated on a 5-point ordinal scale (1=not at all, 2=a little bit, 3=a moderate amount, 4=a great deal, 5=an extreme amount)
- Global Treatment Satisfaction, rated on a 5-point ordinal scale (1=very dissatisfied, 3=neither satisfied nor dissatisfied, 5=very satisfied)

Other Assessments

The following questionnaires will be administered during the study at the Randomization, Week 4, and EOT Visits:

- EuroQol (EQ)-5D-3L
- Work Productivity and Activity Index (WPAI)-GERD-Sleep

Safety Assessments:

Adverse event (AE) recording, clinical laboratory measures (clinical chemistry, hematology, coagulation, and urinalysis), vital sign measurements, ECGs, and physical examinations.

Statistical Methods

Analysis Populations:

Screened Population consists of all patients who signed informed consent and received a patient identification (PID) number.

Randomized Population consists of all patients who were assigned to a treatment group (placebo or IW-3718) via randomization.

Safety Population consists of all randomized patients who received at least 1 dose of study drug.

Modified Intent-to-Treat (mITT) Population consists of all randomized patients who received at least 1 dose of study drug and had at least 1 postbaseline primary efficacy assessment.

General Methods

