3.5.7.2 Weekly Assessments

The following information will be entered into the eDiary once each week during an entry of the evening diary (see Appendix 3):

• Degree of relief assessment

The following items are assessed on a 7-point balanced ordinal scale: 1=Significantly relieved, 2=Moderately relieved, 3=Somewhat relieved, 4=Unchanged, 5=Somewhat worse, 6=Moderately worse, 7=Significantly worse

How would you rate your heartburn (a pain or burning sensation in your chest, behind the breastbone) over the past 7 days?

How would you rate your regurgitation (the feeling of stomach contents, either liquid or food, moving upwards to your throat or mouth) over the past 7 days?

How would you rate your overall GERD symptoms over the past 7 days?

Compared to before you started this study, how would you rate your heartburn (a pain or burning sensation in your chest, behind the breastbone) over the past 7 days?

Compared to before you started this study, how would you rate your regurgitation (the feeling of stomach contents, either liquid or food, moving upwards to your throat or mouth) over the past 7 days?

Compared to before you started this study, how would you rate your overall GERD symptoms over the past 7 days?

Bothersomeness Assessment.

The following items are assessed on a 5-point ordinal scale: 1=Not at all, 2=A little bit, 3=A moderate amount, 4=A great deal, 5=An extreme amount

How much were you bothered by heartburn (a pain or burning sensation in your chest, behind the breastbone) over the past 7 days?

How much were you bothered by regurgitation (the feeling of stomach contents, either liquid or food, moving upwards to your throat or mouth) over the past 7 days?

How much were you bothered by your overall GERD symptoms over the past 7 days?

• Treatment Satisfaction Assessment

The following items are assessed on a 5-point ordinal scale: 1=Very dissatisfied, 2=Dissatisfied, 3=Neither satisfied nor dissatisfied, 4=Satisfied, 5=Very satisfied

How would you rate your satisfaction with the study treatment?

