1. SUMMARY OF THE PROTOCOL AMENDMENT

The major protocol revisions are listed below:

- In accordance with guidance from the US FDA, the primary and key secondary efficacy endpoints have been changed. The analytical methods, including sequential testing to control Type-I error, have been updated accordingly.
- To support the anchor-based analyses corresponding to the 'Change from baseline at Week 8' endpoints, 3 weekly 'Degree of Relief' patient-reported items were added. These 3 new items ask the patient to compare their current degree of relief to that experienced before the start of the study.
- The power calculations for the sample size were recalculated to reflect the new primary and key secondary efficacy parameters.
- Endpoints listed as "Additional Secondary Efficacy Parameters" and the "Additional Efficacy Parameters" were consolidated into a new section "Exploratory Efficacy Parameters". New exploratory endpoints were added.
- Changes were made to one of the study's eligibility criteria for consistency between the synopsis and body of the protocol.
- Enrollment of patients without esophageal erosions was revised to state that the study will aim to enroll up to 50% of patients with esophageal erosions.
- Updates were made to the prohibited medication and concomitant medication guidance.
- The Sponsor's study contact information was updated.

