1. INTRODUCTION

Study C3718-301 is a Phase 3, randomized, double-blind, placebo-controlled, parallel-group, multicenter study of oral IW-3718 administered to patients with gastroesophageal reflux disease (GERD) while receiving proton pump inhibitors (PPIs).

This statistical analysis plan (SAP) describes the statistical analysis methods for all data collected according to the following documents:

- Study Protocol C3718-301 (Amendment 2, dated 14 August 2020).
- Electronic Case Report Form (eCRF) Version 1.0 (dated 27 May 2020).
- Electronic Dairy (eDiary) (dated 10 July 2018)

Specifications for tables, figures, and listings are contained in a separate standard document, the Data Presentation Plan (DPP).

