A corresponding line graph of LS mean with 95% CI by treatment group and Week will be presented. Cumulative distribution function (CDF) of change from baseline at Week 8 in WHSS to be plotted by treatment group. To aid in the interpretation of the graphical representation of the CDF across treatment group, a 2-sample Kolmogorov-Smirnov test will be conducted. If the *P*-value of the Kolmogorov-Smirnov test is small, conclude that the two treatment groups were sampled from populations with different distributions. The populations may differ in median, variability, or the shape of the distribution.

CDF plots of change from Baseline at each week in WHSS by treatment group and patientreported weekly Degree of Relief Assessments (comparing the symptoms over the past 7 days, Appendix 7) classified anchor will be provided. For a sense of variability in the distribution of the classified heartburn relief anchor category, percentile (10th, 25th, 75th and 90th) of change from Baseline to each week in WHSS by treatment group and the anchor will be tabulated.

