Like the primary efficacy parameter, a corresponding line graph of LS mean with 95% CI by treatment group and Week for WRFS will be presented. CDF of change from baseline at Week 8 in WRFS to be plotted by treatment group. To aid in the interpretation of the graphical representation of the CDF across treatment group, a 2-sample Kolmogorov-Smirnov test will be conducted.

CDF plots of change from Baseline at each week in WRFS by treatment group and patientreported weekly Degree of Relief Assessments (comparing the symptoms over the past 7 days, Appendix 7) classified anchor will be provided. For a sense of variability in the distribution of the classified heartburn relief anchor category, percentile (10th, 25th, 75th and 90th) of change from Baseline to each week in WRFS by treatment group and the anchor will be tabulated.

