Appendix 7. Weekly Assessments

Degree of Relief Assessments

Administered weekly during Pretreatment and Treatment Periods:

How would you rate your heartburn (a pain or burning sensation in your chest, behind the breastbone) over the past 7 days?

How would you rate your regurgitation (the feeling of stomach contents, either liquid or food, moving upwards to your throat or mouth) over the past 7 days?

How would you rate your overall GERD symptoms over the past 7 days?

Response Scale for all Degree of Relief Assessments:

- 1=Significantly relieved
- 2=Moderately relieved
- 3=Somewhat relieved
- 4=Unchanged
- 5=Somewhat worse
- 6=Moderately worse
- 7=Significantly worse

Bothersomeness Assessments

Administered weekly during Pretreatment and Treatment Periods:

How much were you bothered by heartburn (a pain or burning sensation in your chest, behind the breastbone) over the past 7 days?

How much were you bothered by regurgitation (the feeling of stomach contents, either liquid or food, moving upwards to your throat or mouth) over the past 7 days?

How much were you bothered by your overall GERD symptoms over the past 7 days?

1=Not at all

- 2=A little bit
- 3=A moderate amount

4=A great deal

5=An extreme amount

Treatment Satisfaction Assessment

Administered weekly during Treatment Period:

How would you rate your satisfaction with the study treatment?

1=Very dissatisfied

2=Dissatisfied

IW-3718 14 January 2021

3=Neither satisfied nor dissatisfied

4=Satisfied

5=Very satisfied

Classification	Definition
Not Present	No breaks (erosions) in the esophageal mucosa. (However, edema, erythema, or friability may be present.)
Grade A	One (or more) mucosal break no longer than 5 mm that does not extend between the tops of two mucosal folds.
Grade B	One (or more) mucosal break more than 5 mm long that does not extend between the tops of two mucosal folds.
Grade C	One (or more) mucosal break that is continuous between the tops of two or more mucosal folds but which involve less than 75% of the circumference.
Grade D	One (or more) mucosal break which involves at least 75% of the esophageal circumference.

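### The SAP's anchor displays for WHSS and WRFS omit the three Degree of Relief items with a pre-study reference, and the WRFS percentile table names the heartburn anchor

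*SAP*

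**What the plan says.** The SAP states that it covers data collected under "Study Protocol C3718-301 (Amendment 2, dated 14 August 2020".

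Protocol 3.5.7.2 and Appendix 3 of that version list six weekly Degree of Relief items, all on one 7-point scale from significantly relieved, through unchanged, to significantly worse. Three ask for a rating over the past 7 days. The other three name a reference point, for example "Compared to before you started this study, how would you rate your overall GERD symptoms over the past 7 days". The synopsis describes these as a "7-point patient global impression of change scale (compared to before you started the study". The Amendment 2 summary of changes gives their purpose: "To support the anchor-based analyses corresponding to the 'Change from baseline at Week 8' endpoints, 3 weekly 'Degree of Relief' patient-reported items were added".

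SAP Table 3 and Appendix 7 list only the first kind, for example "How would you rate your overall GERD symptoms over the past 7 days". SAP 7.9.1.2 plots cumulative distributions of WHSS change at each week by treatment group and by an anchor built from the "Degree of Relief Assessments (comparing the symptoms over the past 7 days", and tabulates percentiles by the same anchor. SAP 7.9.2.1 does the same for WRFS. There the percentile sentence begins "For a sense of variability in the distribution of the classified heartburn relief anchor category".

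**The concern.** An anchor helps interpret change from baseline only if the patient's answer refers to roughly the same change in the same symptom. The past-7-days items leave the comparison to the patient. The items that state it were written for this use, and the SAP neither lists nor analyses them. For WRFS, a literal reading of the percentile sentence sorts regurgitation change by relief of heartburn.

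Anchors have carried weight in this programme. Protocol 1.3 reports that pooled anchor-based analyses pointed to a 45% reduction as the better definition of response, and that threshold now defines Overall Heartburn Responder, a key secondary parameter. At stake is how convincingly a WHSS or WRFS difference can be put in patient terms, and whether the choice of anchor is fixed before unblinding.

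**Working it through.** The plan gives no figure on this point to reproduce. The check compares texts, with some date arithmetic.

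**1. Which items are in which document.** Sources: Protocol 3.5.7.2 and Appendix 3; SAP Table 3 and Appendix 7.

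| Symptom | Past-7-days item | Item with pre-study reference |
|---|---|---|
| Heartburn | Protocol and SAP | Protocol only |
| Regurgitation | Protocol and SAP | Protocol only |
| Overall GERD | Protocol and SAP | Protocol only |

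The protocol has 6 items and the SAP has 3. The missing 6 − 3 = 3 are exactly those with a stated reference.

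**2. What the retained items compare with.** The response scale implies a comparison, but the question does not say with what. SAP Appendix 7 also administers these items in the Pretreatment Period, and SAP 7.3 summarises degree of relief as a baseline characteristic, so at those times the answer cannot mean change since baseline. A week-to-week reading is possible. SAP Table 11 (simulation from 45 Bravo-positive Study ICP-3718-202 patients, placebo and 1500 mg combined) shows why it would matter:

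- Mean WHSS change from baseline: −1.84 at Week 6, −1.84 at Week 7, −1.91 at Week 8.
- Week 7 to Week 8: −1.91 − (−1.84) = −0.07.
- Baseline to Week 8: −1.91.

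On that reading, a patient following the mean course could properly answer unchanged at Week 8 after improving by about 1.9 points. This is an illustration; the documents do not show how patients read the question.

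**3. Which symptom anchors WRFS.** In 7.9.2.1 the sentence on distribution plots names the Degree of Relief Assessments without choosing an item. Only the percentile sentence specifies heartburn relief, in almost the same words as 7.9.1.2. SAP Appendix 7 contains a regurgitation relief item.

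**4. Who could have answered the added items at Week 8.** Inputs: mITT randomisation cut-off 4 August 2020 (SAP 7.1); Amendment 2 dated 14 August 2020; Week 8 window for weekly questions Days 53 to 59 (Protocol Table 5, SAP Table 16); Day 1 is the day of randomisation.

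- The cut-off precedes the amendment by 14 − 4 = 10 days.
- A patient randomised on 4 August was on Day 10 + 1 = 11 at the amendment date. That patient's Week 8 window ran from 4 August + 52 days = 25 September to 4 August + 58 days = 1 October 2020.
- Day 59 falls on 14 August for a patient randomised on 14 August − 58 days = 17 June 2020.

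mITT patients randomised before 17 June 2020 had therefore passed the Week 8 window when the items were introduced. Those randomised from 17 June to 4 August could have answered them only if the eDiary was updated in time. The eDiary version cited in SAP Section 1 is dated 10 July 2018, 766 days before Amendment 2.

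**The case against.** The strongest reply is that the omission has a visible practical reason. The final efficacy analysis uses the mITT Population, which closed ten days before the items were added, and the cited eDiary predates them by two years. For most mITT patients the past-7-days items may be the only anchor available, and the parenthesis in 7.9.1.2 may mark a deliberate choice. This largely stands as an explanation, but the SAP does not give it. The SA Population also includes patients randomised after the cut-off.

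It can also be said that the displays are descriptive, that no meaningful-change threshold is derived from them, and that Protocol 3.7.4 specifies no anchor analysis for the SAP to breach. All of that stands.

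A reader might infer four stronger points, which the documents do not support:

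- **That the past-7-days items cannot serve as anchors at all.** The relieved/unchanged/worse scale implies some comparison, so the reference point is ambiguous rather than absent.
- **That the SAP chose a heartburn anchor for regurgitation throughout.** It is explicit in one sentence, which looks carried over from the WHSS text.
- **That about 660 − 550 = 110 later patients have the added items.** SAP 3.4 gives about 550 as the number to be randomised, and SAP Appendix 1 calls it the study's sample size; neither presents it as the count at the cut-off. SAP Section 4 gives 660. The number with responses could be zero if the eDiary was never updated, and no upper figure can be derived.
- **That a small subset suffices because arms are pooled.** SAP 7.9.1.2 and 7.9.2.1 present the anchors by treatment group.

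**Conclusion.** The mismatch is real and lies between current texts. The SAP cites Amendment 2, runs anchor displays for change from baseline, and leaves out all three items added to support such analyses. The items it uses have an unstated comparison point, and the WRFS percentile table, followed as written, uses the wrong symptom's anchor.

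The size is modest. These outputs are descriptive and lie outside the fixed testing sequence in SAP Table 4, so the primary test, alpha control and power are unaffected.

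Making the added items the main anchor is not justified. It would demote the items available in the mITT in favour of a subset of unknown size, mostly late enrollees. The benefit of analysing the added items assumes that they were deployed in the eDiary, which the documents do not confirm. The WRFS correction does not depend on that assumption.

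**What to change.** 1. In SAP 7.9.2.1, name the regurgitation relief item as the anchor for both the WRFS distribution plots and the WRFS percentile table. In 7.9.1.2, state that the heartburn item is the WHSS anchor.
2. Add the three items with the pre-study reference to SAP Table 3 and Appendix 7. Repeat the anchor plots and percentiles with the item for the matching symptom in all mITT and SA Population patients who have responses, reporting n by week.
3. Keep the past-7-days items as the anchor for mITT patients without the added items, and note their ambiguous reference point. If the added items were never deployed in the eDiary, say so and give that as the reason.

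The change should be made before unblinding, so that the choice of anchor remains prespecified. The cost is SAP wording and one or two more descriptive tables. Precision for the added items is limited by an unknown and possibly small number of patients.

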7.9.1.3. Sensitivity Analysis Based on Multiple Imputation – Missing Not at Random (MNAR)

The analysis specified in this section will be executed only when a superiority result that favors the active treatment group for the primary efficacy parameter is obtained.

To characterize the extent of missing data associated with the primary efficacy parameter, the number and percentage of patients with missing evening diaries will be presented by treatment group for the mITT Population for each week of the Treatment Period.

The primary efficacy analysis (MMRM) relies on the assumption that the missing data mechanism follows the missing at random (MAR) scenario. In this case, it is assumed that the reason for data being missing may depend on observed data, but not on the unobserved missing data. The likelihood based MMRM analysis is an appropriate method for the statistical analysis under MAR assumption.

The following sensitivity analysis model, which are within the pattern-mixture model framework, will be used to examine the robustness of the primary efficacy analysis results for the missing not at random (MNAR) mechanisms. Under MNAR, it is assumed that the reason for data being missing is related to the unobserved missing data.

The imputations are based on the distribution of placebo group responses over time. The underlying assumption is that the missing data for a patient on the active treatment follow the distribution of the placebo responses, i.e., the mean values and intra-subject correlations based on the placebo responses will be applied. Moreover, the intercurrent events will generate MNAR (informative) missing, which will have impact on determining of drug effect. A designated penalty will be prespecified for this type of missing mechanism, in order to adjust the treatment effect estimation to determine a possible "true" treatment effect.

The model is implemented in 4 steps:

Step 1: Imputations

For change from baseline data, a total of 200 sets of posterior mean and co-variance estimates are extracted from the available non-missing placebo data. One hundred of the posterior sets will be applied to the pooled active treatment group, while the other 100 will be applied to the placebo group. One set of imputations for all missing values will be generated based on each variation of posterior estimates. All 100 datasets for imputations within a treatment group will be

ordered from 1 to 100 and combined between pooled active treatment group and placebo, for a total of 100 completely imputed datasets.

Step 2: Adjustments

For patients who have any intercurrent events, a penalty will be designated to the imputed values at the last scheduled visit (Visit 5, Week 8). The penalty is applied to the 2 treatment arms by adding a fraction of the estimated SD for the primary efficacy parameter (the square root of the estimated element for the last scheduled visit of the co-variance matrix R from the primary MMRM model): $(0 \times SD)$, $(0.25 \times SD)$, $(0.50 \times SD)$.

Step 3: Analysis of Complete Datasets

The primary efficacy parameter will be analyzed for each of the 100 complete datasets with imputed and the designated penalty applied data at the last scheduled visit (Visit 5, Week 8), using an analysis of covariance with treatment group as factors and the baseline value as a covariate.

Step 4: Inference

Rubin's Rules will be applied to pool the desired statistical quantities that include LS mean difference estimates, associated 95% CI and p-value, and associated SEs.

Efficacy conclusion of the study is based on the analysis described in Section 7.9.1.2. In the current section, a different missing mechanism is assumed for the data, it is a supportive outcome for the primary efficacy effect analysis.

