- 1. IW-3718 1500 mg compared with placebo
- 2. Patients with no regurgitation at baseline were excluded.

IW-3718 was well tolerated in patients with persistent GERD at twice-daily doses of 500 mg, 1000 mg, and 1500 mg. The most common TEAEs occurring in >5% of IW-3718 patients overall were constipation (8.1% of IW-3718 patients and 7.1% of placebo patients), nausea (6.2% of IW-3718 patients and 2.9% of placebo patients), and flatulence (5.7% of IW-3718 patients and 4.3% of placebo patients). There were 6 total SAEs (2 patients each in the placebo and 1500 mg IW-3718 groups, and 1 patient each in the IW-3718 500 mg and IW-3718 1000 mg groups) - all SAEs were assessed by the Investigator as unrelated to study treatment. Ten patients discontinued the study due to TEAEs, 3 patients each in the placebo, IW-3718 1000 mg, and IW-3718 1500 mg groups, and 1 patient in the IW-3718 500 mg group. No clinically significant changes were attributable to treatment with any of the IW-3718 treatment groups for any hematology, clinical chemistry, coagulation, urinalysis, vital signs, or ECG parameters, other than reduced total cholesterol and LDL-C, which is consistent with the known pharmacologic effects of colesevelam.

Based on the results of the ICP-3718-202 study, a twice-daily dose of 1500 mg IW-3718 was selected for further investigation in 2 Phase 3 trials.

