3.7.4.6 Handling of Missing Data

For the primary efficacy analysis, change from baseline at Week 8 in WHSS, no imputation will be performed on missing data. The WHSS will be computed as the average of daily scores for that week. Rules for the average calculation will be prespecified in the SAP finalized before database lock.

A pattern-mixture model with control-based pattern imputation will be implemented as a multiple imputation method to explore the effects of missing data on the primary efficacy parameter. The details of this approach will be provided in the SAP.

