3.5. Blinding

This is a double-blind study. Ironwood Pharmaceuticals, Inc. (Ironwood, the Sponsor) study personnel, the site investigators, all other site study personnel, and the patient will remain blinded to individual patient treatment assignments throughout the study. Procedures for unblinding in the case of an emergency are included in Clinical Study Protocol C3718-301, Section 3.4.7.

4. **DETERMINATION OF SAMPLE SIZE**

The sample size of 660 patients (330 patients per treatment group) was chosen to ensure adequate power for using the fixed sequence testing method for the primary and key secondary efficacy parameters.

The power calculations for the primary and key secondary efficacy parameters are based on results from patients with evidence of pathological acid reflux (positive baseline Bravo status) in Study ICP-3718-202 that had a similar study population as the current study.

The primary efficacy parameter of the study is the Change from Baseline at Week 8 in Weekly Heartburn Severity Score (WHSS), and key secondary efficacy parameters include:

- Change from Baseline at Week 8 in Weekly Regurgitation Frequency Score (WRFS)
- Overall Heartburn Responder (OHR)
- Proportion of Heartburn-free Days during the 8-week Treatment Period (PHFD)

For definition of the efficacy parameters above, refer to Section 7.9.1.2 and Section 7.9.2.

Using data from patients in Study ICP-3718-202 with similar inclusion/exclusion criteria as the current study, ie, subjects with a positive baseline BRAVO status, we derived the estimated results at end of the study as follows:

Table 1:Study ICP-3718-202 - Summary of Efficacy Parameters at Week 8
(BRAVO+)

Order of Hypothesis Testing	Parameters	Placebo BID (+ PPIs)	1500 mg IW-3718 BID (+ PPIs)
1	Change from Baseline at Week 8 in WHSS	N = 43 Mean = -1.58 SD = 1.20	N = 51 Mean = -2.01 SD = 1.29
2	Change from Baseline at Week 8 in WRFS	N = 43 Mean = -0.81 SD = 1.12	N = 51 Mean = -1.26 SD = 0.91
3	Overall Heartburn Responder	18/49 = 36.7%	31/55 = 56.4%
4	Proportion of Heartburn-free Days during the 8-week Treatment Period	N = 48 Mean = 0.195 SD = 0.2822	N = 55 Mean = 0.268 SD = 0.2928

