7.2. Patient Disposition

The number and percentage of screen failure patients (ie, patients who entered the Screening Period but not the Pretreatment Period), the number and percentage of pretreatment failures (ie, patients who entered the Pretreatment Period but were not randomized), along with the associated reasons for failure, will be tabulated overall for the Screened Population. Patients who initially failed screening and were re-screened will only be counted once, that is, the PID used for the rescreened patients will be listed for patient disposition, while the PID assigned for the original screening will not be analyzed or listed.

The number and percentage of randomized patients who were included in the Safety Population, who were included in the mITT Population, who completed the Treatment Period, and who prematurely discontinued treatment will be presented overall and by treatment group. A patient is considered to have completed the Treatment Period if the patient completed the 8 weeks of treatment and the EOT Visit that was recorded on the end-of-treatment eCRF page. The reason for premature discontinuation as recorded on the eCRF will also be summarized by treatment group and overall.

The number and percentage of patients who prematurely discontinued treatment will be presented for each treatment group by time of discontinuation, defined as the week (Week 1 through Week 8) in which the treatment discontinuation occurred.

The number of patients screened, the number and percentage of patients randomized will be presented by study center within each geographic region (See Appendix 3 for the definitions of

the geographic regions). A separate disposition table will be generated to include the SA Population and other relevant information.

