7.9.1. Primary Efficacy Parameter

7.9.1.1. Estimands

The primary efficacy estimands that are prepared to support regulatory decisions, are described below.

The **While on Treatment Strategy** for the primary efficacy parameter will be used. It is defined by the following:

- Treatment: intervention IW-3718 (1500 mg), while receiving PPIs.
- **Population**: patients in the mITT with GERD who continue to have persistent symptoms, such as heartburn and regurgitation, while receiving once-daily (QD), standard-dose PPIs.

- Variable: Weekly Heartburn Severity Score (WHSS) derived for each treatment visit. The WHSS for a week is the average of the non-missing Daily Heartburn Severity Scores (DHSS) for that week.
- **Intercurrent event**: the following intercurrent events will be considered:
 - a. Discontinuation of treatment due to lack of efficacy
 - b. Lost to follow-up
 - c. Discontinuation of treatment due to AE
 - d. Discontinuation in the study by physician's decision
 - e. Withdrawing consent
 - f. Withdraw due to protocol violations
- **Population-level summary**: mean difference in change from baseline between treatment groups.

Henceforth, for simplicity, background therapy PPIs will be omitted when referring to study drug treatment (IW-3718 and placebo).

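### The MNAR penalty in SAP 7.9.1.3 has no rule for pairing levels across arms; a shared level adds no dependable stress, and the Step 3 model drops the stratification factors

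*SAP*

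**What the plan says.** SAP 7.9.1.3 runs only if the primary analysis shows superiority of IW-3718. Its model "will be used to examine the robustness of the primary efficacy analysis results for the missing not at random (MNAR) mechanisms". Step 1 imputes missing values in both arms from placebo data; for IW-3718 patients, "the mean values and intra-subject correlations based on the placebo responses will be applied". This delivers what Protocol 3.7.4.6 promised: "A pattern-mixture model with control-based pattern imputation will be implemented as a multiple imputation method", with details left to the SAP.

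Step 2 then adds a penalty to the imputed Week 8 values of patients with any intercurrent event: "The penalty is applied to the 2 treatment arms by adding a fraction of the estimated SD for the primary efficacy parameter". The fractions are 0, 0.25 and 0.50, and the SD is the Week 8 value from the covariance matrix of the primary MMRM. The events are those of SAP 7.9.1.1, where "the following intercurrent events will be considered" introduces six reasons for stopping treatment or leaving the study. Neither document says whether the arms share a level in each run, are crossed, or vary separately.

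Step 3 fits an ANCOVA with treatment and baseline value only. SAP 6.2 says efficacy analyses are adjusted for EE status and baseline WHSS category, and the primary MMRM in 7.9.1.2 contains both.

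**The concern.** A delta penalty tests robustness when it makes the unobserved active-arm outcomes worse than the imputation model assumes and leaves the comparator alone. If the same amount is added in both arms, the two penalties offset each other, and what remains depends on which arm has more penalised patients.

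Near-equal shares are plausible. In the Phase 2b study, "Ten patients discontinued the study due to TEAEs, 3 patients each in the placebo, IW-3718 1000 mg, and IW-3718 1500 mg groups". Stable results at 0, 0.25 and 0.50 SD could then be reported as robustness under MNAR when they show only that dropout was similar. If placebo has more dropout, the penalty improves the IW-3718 result. Because the section runs only after a positive primary result, an unstated pairing rule would also be settled once that result is known.

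The Step 3 omission is separate and smaller. With different covariates, a difference from the primary estimate no longer reflects the missing-data assumption alone.

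**Working it through.** **Inputs.** SAP Section 4, Table 1: placebo "N = 43 Mean = -1.58 SD = 1.20"; IW-3718 N = 51, mean -2.01, SD 1.29. The planned difference is -2.01 - (-1.58) = -0.43; negative favours IW-3718. SD = √((1.20² + 1.29²)/2) = 1.246. The SAP's SD is the MMRM value, which may be smaller; at an assumed baseline correlation of 0.5 it is 1.246 × √0.75 = 1.08. Sample size is 330 per arm (SAP Section 4) or 275 (SAP 3.4 and Appendix 1 mention about 550 in total). Appendix 1 puts Phase 2b discontinuation at about 10%. Every missing Week 8 value is assumed to belong to a patient with an intercurrent event.

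**The plan's own figure.** SE = 1.246 × √(2/330) = 0.0970; 0.43/0.0970 = 4.43; two-sided power at 0.05 is 99.3%, matching the stated 99% or so. The SAP gives no figure for the penalty analysis itself.

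**Formulas.** Let dA and dP be the penalised shares on IW-3718 and placebo, and k the fraction.

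- After Step 1, with a full jump to the placebo mean: -0.43 × (1 - dA).
- Shared level adds k × SD × (dA - dP).
- IW-3718-only level adds k × SD × dA.
- Variance per arm is SD² + d(1 - d)(k × SD)², with the second term only where a penalty applies.

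**Results** (SD 1.246, 330 per arm; difference, z in absolute value). The 7.3% (4/55) and 12.2% (6/49) shares are inferred from Table 1 as responder denominators minus Week 8 Ns. They are not reported dropout rates, so they are also shown reversed.

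| Shares IW-3718 / placebo | Penalty on | 0 SD | 0.25 SD | 0.50 SD |
|---|---|---|---|---|
| 10% / 10% | both | -0.387, 3.99 | -0.387, 3.98 | -0.387, 3.95 |
| 10% / 10% | IW-3718 only | -0.387, 3.99 | -0.356, 3.66 | -0.325, 3.33 |
| 20% / 20% | both | -0.344, 3.55 | -0.344, 3.53 | -0.344, 3.48 |
| 20% / 20% | IW-3718 only | -0.344, 3.55 | -0.282, 2.90 | -0.219, 2.24 |
| 7.3% / 12.2% | both | -0.399, 4.11 | -0.414, 4.26 | -0.430, 4.38 |
| 12.2% / 7.3% | both | -0.377, 3.89 | -0.362, 3.72 | -0.346, 3.53 |

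The unequal-share shift at 0.50 SD is 0.623 × 0.0497 = 0.031 in size, or 0.031/0.097 = 0.32 of an SE. At SD 1.08 it is 0.027.

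**Simulation check.** 150 trials, 330 per arm, 100 placebo-based imputations, ANCOVA on treatment and baseline (assumed correlation 0.4 in size), Rubin's rules, 10%/10%. Shared level: -0.399 throughout, |t| 4.27, 4.24, 4.19. IW-3718 only: -0.399, -0.371, -0.342, |t| 4.27, 3.94, 3.61.

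**Where would an IW-3718-only penalty remove significance?** Imputation that conditions on a patient's earlier weeks keeps a part f of the effect, so the Step 1 estimate is effect × (1 - dA(1 - f)). f = 0 is the full jump; f reached 0.77 across a range of assumed correlation structures and dropout timings. With dA = 0.10, the loss point is k = (|Step 1 estimate| - 1.96 × SE)/(SD × 0.10), ignoring extra imputation variance. At an assumed effect of -0.25, which is not in the documents, the Step 1 estimate is -0.225 (f = 0) to -0.2443 (f = 0.77):

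| n per arm | SD | 1.96 × SE | k at f = 0 | k at f = 0.77 |
|---|---|---|---|---|
| 330 | 1.246 | 0.190 | 0.28 | 0.43 |
| 330 | 1.08 | 0.165 | 0.56 | 0.74 |
| 275 | 1.246 | 0.208 | 0.13 | 0.29 |
| 275 | 1.08 | 0.180 | 0.41 | 0.59 |

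At -0.43 and 10% missing, the smallest loss point is (0.387 - 0.208)/0.1246, about 1.43 SD (275 per arm, SD 1.246, f = 0).

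**Step 3.** With 45% EE (SAP Section 4), omitting EE status inflates the SE by √(1 + b² × 0.45 × 0.55/SD²) for an assumed EE effect of b points: 1.001 at b = 0.1, 1.007 to 1.010 at 0.3, and 1.020 to 1.026 at 0.5.

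**The case against.** The case for leaving Step 2 alone has several parts.

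- **It is supportive only.** The SAP says the efficacy conclusion rests on 7.9.1.2, and at -0.43 none of the listed levels changes significance. This stands and limits the weight of the point.
- **Step 1 already supplies directional stress.** It imputes IW-3718 dropouts from placebo, as the protocol promised, and neither document commits to an active-only or tipping-point run. This also stands: at 10% missing, Step 1 alone moves -0.43 to -0.387 under a full jump. But Step 2 is presented as a further adjustment for informative dropout, and a shared level does not dependably provide one.
- **A common penalty is coherent.** It treats an intercurrent event as a bad outcome in either arm and does count against IW-3718 if that arm has more events. That is true, but the test then depends on the dropout split. A reader can see the split, since "The number and percentage of patients who prematurely discontinued treatment will be presented for each treatment group by time of discontinuation", but a table does not replace a run that penalises IW-3718 alone.
- **The numerical impact rests on assumptions.** The -0.25 effect is assumed. At SD 1.08 and 330 per arm the loss point lies beyond 0.50 SD. Intermittent diary gaps need not be penalised, so the shares may be overstated. The Phase 2b shares rest on 4 and 6 patients (Fisher p = 0.51), and the 3-versus-3 count covers only one of six events. All of this is fair; the cancellation itself depends on none of it.
- **Step 3 is minor.** SAP 6.2 could be read as applying anyway, and continuous baseline WHSS carries much of its category. Agreed on size; the text still conflicts.

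**Conclusion.** The concern holds. Step 2 gives no pairing rule. Crossed levels are not excluded, but a shared level is the natural reading, and under it the 0.25 and 0.50 SD runs leave the estimate unchanged at equal shares and move it either way otherwise, by about 0.031 points at 0.50 SD with the inferred Phase 2b shares. That is small, and it decides nothing at the planned effect. It would matter for a smaller positive result: at an assumed -0.25 with 10% missing per arm, the loss point for an IW-3718-only penalty may fall inside or outside the listed 0.50 SD, and the plan as naturally read would not show which. These sizes rest on the Phase 2b SDs, the assumed missing shares, and treating all missing Week 8 values as penalised.

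The Step 3 model does conflict with SAP 6.2 and the primary model, at a cost of roughly 0.1% to 2.6% of the SE for assumed EE effects of 0.1 to 0.5 points. Type I error, the zero-penalty analysis and the primary conclusion are untouched. The change should be made, but the trial's main inference does not depend on it.

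**What to change.** Keep Step 1 as written. In Step 2, set out a two-way grid of penalties by arm that includes IW-3718 penalised with placebo at 0, and extend it until significance is lost, so that the report gives a tipping point. Fix this before unblinding. In Step 3, add EE status and baseline WHSS category (<3 versus ≥3) to the ANCOVA, to match SAP 6.2 and the primary model.

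The cost is SAP wording and some additional analyses of the imputed data. The supportive result may look less favourable to IW-3718. The primary analysis does not change.
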